6.14.7.2. Tertiary/Exploratory Safety Analyses

The following exploratory safety endpoints will also be analyzed using an MMRM model adjusting for baseline reading:

- daily average change in HBPM measurements and PR from baseline to Week 12
- change in MDS-UPDRS items 4.1 and 4.2, time with dyskinesias, and impact of dyskinesias
- change in item 1.2 (hallucinations/psychosis) score of the MDS-UPDRS Part IA from baseline to Week 12
- change in score for the delusion (Part A) and hallucinations (Part B) domains of the NPI from baseline to Week 12
- change in QUIP score from baseline to Week 12, and
- change in PWC-20 total score will be analyzed using an analysis of covariance (ANCOVA) model with a covariate for baseline score. The primary analysis will be a change from baseline (Visit 11) to the in-person follow-up visit (Visit 801).

6.14.7.3. Home Blood Pressure Monitoring Analyses

Change from baseline in (i) average daily, (ii) morning, and (iii) evening home BP and PR to Week 3 will be analyzed using an MMRM with fixed effects for baseline value, treatment, day, and treatment by day and baseline by day interaction terms with repeated measures of day within subject. The baseline value for each analysis will be defined as the average of all relevant samples taken prior to first dose of LY3154207. A similar analysis will be completed for the 7 days before and after last dose. The MMRM analysis of the HBPM will provide daily estimates of change from baseline for the first 3 weeks of treatment. If there is a rise in BP and PR, the duration taken to accommodate can be assessed using the daily estimates of change from baseline. Visualizations will be used to characterize the temporal course of BP and PR changes, including accommodation. Additional exploratory analyses may be considered as necessary to further characterize the cardiovascular effects of LY3154207.

6.14.7.4. Addendum Safety Analyses

ABPM Addendum Objective

The objectives of the ABPM assessments are to explore any diurnal effects of LY3154207 on SBP and PR in subjects with PDD and whether these diurnal effects change over the study period—in particular, to evaluate the effect of LY3154207 on nocturnal dip in SBP.

ABPM Analysis

Only subjects participating in the ABPM addendum will be included in this analysis. The ABPM results will be summarized and represented graphically.

The ABPM will be used to assess the effect of LY3154207 on the dip in nocturnal SBP. A nocturnal dip is defined as a greater than 10% reduction in average SBP during the night compared to the average during the day. In order to reduce variability in the subject's sleep and awake period, the nighttime is defined as 0100 hours to 0600 hours. Similarly, the daytime, for purposes of analysis, is defined as 0900 hours to 2100 hours, when most subjects would be

expected to be awake, and the morning surge is defined as the mean of 4 readings over a period of 2 hours after subjects wake up from the lowest nocturnal SBP (mean of 3 readings centered around the lowest nighttime SBP). For each ABPM assessment period following dose administration (assessments will be between Visits 3 and 4, between Visits 7 and 8, and between Visits 10 and 11), the proportion of subjects who have a nocturnal dip will be summarized by treatment group, and a logistic regression will be performed to evaluate any treatment effect. The regression model will include the % reduction in SBP at baseline (measured between Visits 2 and 3) as a covariate. Odds ratios and associated 95% CIs will be presented.

Individual subject time courses will be reviewed graphically to investigate whether there is any morning surge effect.

In addition, the 24-hour average and the daytime and nighttime average SBP and PR changes from baseline at each ABPM assessment period will be analyzed using an MMRM analysis. Only the first 24 hours of data collected for each ABPM assessment period will be included. This will assess for any treatment effects and if there are any, whether they accommodate over the trial. The analyses will include fixed effects for baseline value, visit, treatment, treatment by time and baseline by time interaction with repeated measures of visit within subject. The time variable relates to the ABPM assessment period and will be assigned value of 1, 2, 3, or 4. An unstructured covariance matrix will be considered initially; however, if this fails to converge, other suitable structures will be considered. Baseline values will be defined as the 24-hour mean of the recordings taken following Visit 2; the mean of the recordings taken between 0900 hours to 2100 hours following Visit 2; and the mean of the recordings taken between 0100 hours to 0600 hours following Visit 2.

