6.7. Multiple Comparisons/Multiplicity

No adjustments will be made for multiple comparisons.

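### The nocturnal SBP dip, the ABPM addendum's particular target, is tested only as yes/no at a 10% cut; no planned analysis gives an interval for the size of the dip or tests whether the effect changes over time

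*SAP*

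**What the plan says.** The ambulatory (ABPM) section, SAP 6.14.7.4, sets out to explore diurnal effects on SBP and pulse rate and whether they change during the study, "in particular, to evaluate the effect of LY3154207 on nocturnal dip in SBP".

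- **Definition.** "A nocturnal dip is defined as a greater than 10% reduction in average SBP during the night compared to the average during the day". Night is 0100 to 0600 hours and day is 0900 to 2100 hours.
- **Analysis of the dip.** For each of the three post-dose periods (Visits 3 to 4, 7 to 8 and 10 to 11), "the proportion of subjects who have a nocturnal dip will be summarized by treatment group, and a logistic regression will be performed". Baseline percent reduction enters this regression as a continuous covariate, and the results are to be reported as odds ratios with 95% intervals.
- **Other ABPM analyses.** An MMRM is planned for "the 24-hour average and the daytime and nighttime average SBP and PR changes from baseline at each ABPM assessment period", with treatment by time and baseline by time interactions. SAP 6.2 attaches 95% intervals to MMRM treatment differences in general. Results are also shown graphically.
- **Multiplicity (SAP 6.7).** "No adjustments will be made for multiple comparisons".

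Only addendum participants are included. The documents give no ABPM sample size, dipper share, SD of percent dip or power for this analysis.

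**The concern.** Percent night-to-day reduction has to be calculated for every addendum participant in every period before the 10% cut can be applied. The plan uses it in continuous form at baseline and then dichotomises it as the outcome. Cutting a continuous measure costs precision, and here it affects the one outcome that the addendum singles out. The other planned treatment comparisons of blood pressure, in-clinic (SAP 6.14.7.1), home (6.14.7.3) and ABPM means (6.14.7.4), all use continuous change in an MMRM.

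The stated aim also includes change over the study. A separate logistic regression in each period has no treatment by period term, so no specified model asks whether an effect on the dip grows or accommodates. This is a safety question in a subset split over four arms, so avoidable imprecision makes a real loss of dip harder to see.

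**Working it through.** The plan states no figure for this analysis, so there is none to reproduce. The check has two parts.

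**1. Does any planned analysis give an interval for the size of the dip?**

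- The logistic regression gives an odds ratio with a 95% interval, for crossing 10%. It does not describe how far the dip moves.
- The MMRM treats daytime and nighttime means as separate responses. Subtracting the two treatment effects gives roughly the effect on absolute dip in mm Hg. An interval for it needs Var(night − day) = Var(night) + Var(day) − 2 Cov(night, day), and two separate models do not supply the covariance term.
- The treatment by time term applies to those separate means, not to the dip.

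So neither the size of the effect on the dip nor its change over periods has a planned inferential analysis.

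**2. How much precision does the cut cost?**

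Assumptions, none of them from the documents: percent dip is normal, treatment shifts only its mean, and the dipper share p is 10% to 50%. Shares of 50% to 90% mirror these.

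Relative efficiency of the yes/no analysis = φ(z_p)² / [p(1 − p)].

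| Dipper share p | φ(z_p) | φ² / [p(1 − p)] | Efficiency | Subjects needed, as a multiple (1 / efficiency) |
|---|---|---|---|---|
| 50% | 0.399 | 0.159 / 0.25 | 0.64 | 1.6 |
| 30% | 0.348 | 0.121 / 0.21 | 0.58 | 1.7 |
| 20% | 0.280 | 0.078 / 0.16 | 0.49 | 2.0 |
| 10% | 0.175 | 0.031 / 0.09 | 0.34 | 2.9 |

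The loss is therefore 36% to 66%. Under this model it is never below 36%.

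*With baseline percent reduction in both models.* Let ρ be the baseline to follow-up correlation, e = (z_p + ρx)/√(1 − ρ²) and P = Φ(e). Averaging φ(e)²/[P(1 − P)] over a standard normal baseline x gives efficiency 0.57 (p = 50%) to 0.29 (p = 10%) at ρ = 0.5. At ρ = 0.7 it is 0.49 to 0.24. The unadjusted range is, if anything, favourable to the cut.

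*Finite shift, illustrative.* For a 0.5 SD shift, 80% power and two-sided 5%, the continuous comparison needs 2 × (1.960 + 0.842)² / 0.5² = 62.8, so 63 per arm. The yes/no comparison needs the following, with the range covering both directions of shift:

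- p = 50%: 102 per arm
- p = 30%: 103 to 126
- p = 20%: 115 to 160
- p = 10%: 152 to 256

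At an assumed 20 per arm, power is 35% for the continuous analysis and 16% to 23% for yes/no (p = 20% to 50%).

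**The case against.** The strongest reply is that the SAP defines the dip as a binary event and analyses that event with an interval, so the prespecified question is answered. That is right as far as it goes. A reader might infer that the dip has no interval at all, and the documents do not support that: the odds ratios carry 95% intervals. What is missing is an interval for the dip's magnitude.

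A reader might also infer that a third to two thirds of the ABPM information is thrown away. That is too broad. The loss concerns the dip test alone, because 24-hour, daytime and nighttime means are all analysed uncut. The range itself depends on an assumed dipper share.

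Nor is an adverse shift invisible. One subject moving from 9% to 2% stays a non-dipper, but the analysis compares groups. With an assumed SD of 5 to 10 points, a fall in mean dip from 9% to 2% moves the dipper share from about 42–46% to 6–21%. A fall from 20% to 11% moves it from about 84–98% to 54–58%. The nighttime MMRM would respond too: with an assumed stable daytime mean of 130 mm Hg, these falls are nighttime rises of 0.07 × 130 ≈ 9 mm Hg and 0.09 × 130 ≈ 12 mm Hg.

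Finally, the addendum is exploratory, no stated decision rule rests on it, and SAP 6.2 and 6.14.7.3 leave room for extra exploratory work. This limits the consequence. But permission to explore does not specify the analysis that the objective calls for.

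**Conclusion.** The point holds as an opportunity to gain precision in an exploratory safety analysis. It is not an error in any stated figure. The dip is tested only at the 10% cut, period by period, and no planned analysis gives an interval for the effect on its size or tests whether that effect changes across periods. With normal percent dip and a dipper share of 10% to 50%, the dip test keeps about 34% to 64% of the information in a continuous analysis, and somewhat less when both analyses adjust for baseline. These figures rest entirely on assumed inputs. They describe reduced sensitivity of one test, not a blind spot in the ABPM data. The addendum itself is not among the documents, so the number of participants is unknown and absolute power cannot be stated.

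**What to change.** Add change from baseline in percent nocturnal SBP reduction as one more response in the MMRM already specified in SAP 6.14.7.4, with baseline percent reduction as covariate and a treatment by period term. Report each dose's difference from placebo with a 95% interval in each post-dose period, and the treatment by period test.

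Keep the 10% dipper proportion and its logistic regression as prespecified. The continuous analysis complements them, and there is no need to demote them.

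The SAP's revision history says that the current version was approved after unblinding. If the analysis is added now, label it supplementary.

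The cost is small: no new data or visits, and one more run of an existing model. The downside is one more set of exploratory, unadjusted comparisons (3 doses × 3 periods = 9 intervals), to be read as estimates.

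### The SAP gives the morning surge in SBP a numeric basis but names only visual review of individual curves for it, so no between-arm surge estimate is specified

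*SAP*

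**What the plan says.** SAP 6.14.7.4 (ABPM Analysis) describes the surge in part of one sentence: "the morning surge is defined as the mean of 4 readings over a period of 2 hours after subjects wake up", taken from the lowest nocturnal SBP, which is itself the "mean of 3 readings centered around the lowest nighttime SBP". Its analysis is a separate single sentence: "Individual subject time courses will be reviewed graphically to investigate whether there is any morning surge effect".

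The other ABPM quantities are handled differently. For the nocturnal dip, the proportion of subjects with a dip is summarised by arm in each of three post-dose periods, and "a logistic regression will be performed to evaluate any treatment effect", with the baseline percentage reduction as covariate and odds ratios with 95% CIs. The 24-hour, day and night averages of SBP and PR get an MMRM of their change from baseline in each period, with a baseline term.

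The windows behind those averages are fixed clock times: "the nighttime is defined as 0100 hours to 0600 hours", and the daytime "is defined as 0900 hours to 2100 hours, when most subjects would be" awake. A general sentence promises a summary and plots of the ABPM results. It does not mention the surge or a comparison of arms.

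**The concern.** A quantity with a numeric basis can be computed for each subject in each recording period and compared between arms with adjustment for baseline. Inspecting individual curves gives no estimate, no interval, no allowance for the pre-dose surge and no rule for deciding that an effect is present. Of the ABPM quantities that the section defines, only the surge is left in that position.

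The question is not remote from the section's purpose. The ABPM objective covers diurnal effects on SBP and whether they change over the study. Protocol 7.2 has study drug taken in the morning, and SAP 5.2 lists ABPM among the measures for judging whether an early rise in BP settles. If the drug altered the surge relative to placebo, the planned output would hold plots and a visual impression, with no comparative figure for any of the three post-dose periods.

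**Working it through.** The documents state no sample size, SD, power or precision for the ABPM addendum, so there is no figure to reproduce. The check is whether another planned ABPM model already isolates the post-waking window.

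**Inputs from SAP 6.14.7.4.** Night runs from 0100 to 0600 (5 h), day from 0900 to 2100 (12 h), and the surge window is the 2 h after waking. Waking time is not given, so a range is assumed.

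**Step 1: coverage.** Day and night together cover 12 + 5 = 17 of 24 hours. The other 7 hours are 0600 to 0900 (3 h) and 2100 to 0100 (4 h).

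**Step 2: surge window against the two averages.** Uncovered hours = 2 − overlap with night − overlap with day.

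| Assumed waking time | In night average (h) | In day average (h) | In neither (h) |
|---|---|---|---|
| 0500 | 1.0 | 0 | 1.0 |
| 0530 | 0.5 | 0 | 1.5 |
| 0600 to 0700 | 0 | 0 | 2.0 |
| 0730 | 0 | 0.5 | 1.5 |
| 0800 | 0 | 1.0 | 1.0 |
| 0830 | 0 | 1.5 | 0.5 |
| 0900 | 0 | 2.0 | 0 |

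The full window is missed only for waking between about 0600 and 0700. Part of it is missed for other waking times from 0500 up to 0900. Even at 0900, where it is fully inside the day average, it is 2/12 = 17% of that average.

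**Step 3: dilution in the 24-hour mean.** That mean does include the window, with weight 2/24 = 8.3% if readings are evenly weighted over the day. A drug-placebo difference D confined to those 2 hours shifts the mean by D × 2/24:

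- D = 5 mmHg: 0.42 mmHg
- D = 10 mmHg: 0.83 mmHg
- D = 15 mmHg: 1.25 mmHg
- D = 20 mmHg: 1.67 mmHg

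**Step 4: scale.** The nearest stated precision is in SAP 5.2, for average SBP at the 6- and 12-week assessments: SD 10 mmHg and 20% discontinuation. With 85 per arm, 85 × 0.8 = 68 remain, and the 95% half-width is 1.96 × 10 × √(2/68) = 3.36 mmHg, consistent with the stated bound of 3.5. If that SD also applied to the 24-hour mean (an assumption), even full arms would give a half-width about four times the 0.83 mmHg shift (3.36/0.83 ≈ 4.0). This is an illustration only, since the SD of the 24-hour ABPM mean is not given.

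**Step 5: models outside the ABPM section.**

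- SAP 6.14.7.3 compares morning home BP between arms day by day to Week 3, with a similar analysis for the 7 days before and after the last dose. Protocol 9.4.2 places those seated readings right after dosing, with no nocturnal reference.
- SAP 6.14.7.1 compares in-clinic BP over the 8 hours after the first dose, and the 0 to 6 hour averages at Weeks 6 and 12. These are timed from dosing, not from waking, and also have no night reference.

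Neither measures a rise from the night-time low to the post-waking level.

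**The case against.** The strongest reply is that morning BP is well covered. The 24-hour MMRM includes the post-waking hours and compares treatments, and home and in-clinic BP have their own treatment comparisons. That stands against two stronger readings a reader might infer. The first is that the ABPM section leaves the hours after waking with no placebo comparison at all. The documents do not support this, because those hours are in the 24-hour average, though diluted. The second is that the trial would overlook a rise in BP in the morning. The documents do not support this either, given the home and in-clinic models. What is missing is narrower: an estimate of the surge itself.

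The fixed windows are also deliberate. The SAP chose them to limit variability from differing sleep and wake times, and the late-evening hours are left out as well. Omitting transition hours is therefore not an error in the day and night averages. It means only that those averages cannot stand in for a surge analysis.

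Third, the section is exploratory, its objective singles out the nocturnal dip, and the surge is not a named objective. Plots for a secondary feature in a subset of subjects are a defensible choice. This limits the importance of the point but does not explain why a quantity is built from specified readings and then not computed by arm.

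Finally, the definition is incomplete. It names two means without saying that one is subtracted from the other, and the SAP does not say how waking time is recorded. The ABPM protocol addendum, where such details may sit, is not among the documents. This stands and is taken into the fix.

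**Conclusion.** The point holds in a limited form. The SAP specifies no treatment contrast, interval or baseline adjustment for the surge, and none of the other ABPM models isolates the window. The dilution figure, about 0.8 mmHg in the 24-hour mean for each 10 mmHg confined to the 2 hours, assumes an effect limited to that window and even weighting over the day. How much of the window the day and night averages miss depends on waking time, from none at 0900 to all of it at 0600 to 0700.

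A reader might go on to put a figure on lost power by treating visual review as a yes/no classification. The documents do not support one: the SAP plans no such test, and neither the ABPM subset size nor the SD of the surge is given. For the same reason, the precision of the proposed estimate cannot be stated. Nor is a comparison impossible, since the readings exist in every arm; the plan simply does not commit to making it.

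The matter is minor. It concerns an exploratory safety question and does not touch the primary result.

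**What to change.** In SAP 6.14.7.4:

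1. State the surge as the post-waking mean minus the lowest-night mean, per subject and ABPM period.
2. State how waking time is obtained, and what happens when it is missing or when too few readings are available.
3. Say whether the rule restricting the MMRM to the first 24 hours of each recording applies, since it could cut off the post-waking readings depending on the start time.
4. Add the surge as a further response in the MMRM already planned for the 24-hour, day and night averages, with the surge from the recording between Visits 2 and 3 as the baseline covariate.
5. Report LS mean differences from placebo with 95% CIs for each post-dose period, labelled exploratory, and keep the individual plots as support.

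The cost is a few sentences and one more run of an existing model. No new data are needed if waking time is recorded, which the current definition already requires; if it is not, the definition cannot be applied as written. The downside is one more exploratory safety contrast without multiplicity adjustment, in line with SAP 6.7.

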6.15. Subgroup Analyses

Change in CoA, ADAS-Cog₁₃, and CGIC from baseline to Week 12 may be assessed based on the following subgroups: concomitant PD therapy; use of concomitant AChEI therapy; use of memantine therapy; mild/moderate cognition (moderate: 10-16 total MoCA score; mild: 17-23 total MoCA score); and timing of dementia onset (less than or equal to 1 year versus greater than 1 year relative to onset of motor symptoms). These analyses will involve running the analysis outlined in Section 6.12.1 on subsets of the EPP according to each level of each variable listed above separately.

All subgroup analyses will be considered exploratory, and additional subgroup analyses may be performed as suggested by the data.

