10.3.6. Other Analyses

10.3.6.1. Subgroup Analyses

The CDR-CCB CoA and its component scores will be assessed based on the following subgroups: concomitant PD therapy, concomitant AChEI therapy, PDD or DLB, and GDS (less than or equal to 6). All subgroup analyses will be considered exploratory and additional subgroup analyses may be performed as suggested by the data.

[figure not shown]

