5.2. Determination of Sample Size

Approximately 750 subjects will be screened to achieve 340 randomized subjects. The randomization will be 1:1:1:1 to LY3154207 (10, 30, or 75 mg QD) or placebo treatment arms.

CCI

If the true effect size for LY3154207 relative to placebo on the CoA is 0.4 with the sample size of 340, there will be greater than 80% probability of passing this criterion. A 20% discontinuation rate by Week 12 has been accounted for in the sample size determination.

Sample size estimation was based on an article by Wesnes et al. (2005) where the difference in mean change from baseline for rivastigmine compared to placebo and the pooled standard deviation (SD) for CoA were estimated as 5.7 units and 18 units, respectively. The rivastigmine effect corresponded to a reduction in the deficit of subjects compared to age-matched healthy volunteers of approximately 45%. Based on this result, the effect size of 0.4 in this study corresponds to a mean difference of 7.2 units (approximately 57% reduction in the deficit).

This sample size will allow assessment of the in-clinic blood pressure (BP) and pulse rate (PR) values on the first day of dosing in order to evaluate any changes after the first dose of treatment that was seen in Phase 1. If the SD of the in-clinic systolic blood pressure (SBP) value is assumed to be 15 mm Hg, then the difference from the mean to the upper limit of a 95% confidence interval (CI) of the change from baseline in SBP relative to placebo is expected to be <4.7 mm Hg. If there is any initial rise in BP or PR, the in-clinic 6- and 12-week assessments along with the home blood pressure monitoring (HBPM) and ambulatory blood pressure monitoring (ABPM) measures will be used to assess whether the rise accommodates. The difference from the mean to the upper limit of a 95% CI in the change in average SBP measured at each of these visits relative to placebo is expected to be <3.5 mm Hg. This assumes an SD of 10 mm Hg and a 20% discontinuation rate.

Simulations were conducted in FACTs Version 5.1.1 using a Bayesian normal dynamic linear model (NDLM).

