6.12. Efficacy Analyses

6.12.1. Primary Outcome and Methodology

The primary objective is to evaluate whether LY3154207, administered at 10 mg, 30 mg, and/or 75 mg QD oral dosing for 12 weeks, will show an improvement in cognition compared to placebo in subjects with mild-to-moderate LBD. This objective will be assessed in the EPP using a Bayesian MMRM analysis of the change in the CDR-CCB CoA data from baseline to Week 12. Continuity of Attention (CoA) is defined as the sum of correct responses from the Choice Reaction Time and Digit Vigilance Task with the number of Digit Vigilance Errors subtracted.

The primary analysis on CoA will occur when all subjects have had the opportunity to complete 12 weeks of treatment.

The analysis of CoA will utilize a Bayesian MMRM model. The Bayesian analysis will use uninformative priors for all terms in the model. For the model coefficients, these will be diffuse Normal distributions centered on zero. Prior for covariance matrix will follow an inverse-Wishart distribution (the multivariate generalization of an inverse gamma distribution for a variance component). The MMRM model will account for longitudinal data assessed throughout the study after 1, 2, 4, 6, 8, 10, and 12 weeks of dosing. The change in CoA from baseline to Week 12 will be the dependent variable. The model will comprise fixed (baseline value, treatment, visit, age, and use of AChEIs) with the interaction terms (treatment by visit, baseline value by visit) with repeated measures of visit within subject. Visit will be considered a categorical variable with values equal to the visit numbers at which the CoA was assessed. Covariates may be centered prior to analysis to aid model convergence.

The primary comparison will be the contrast between treatments and placebo for the Week 12 change from baseline against a null hypothesis of no difference. This will be presented as both a difference in estimated means of the 12-week change and the effect sizes over the 12 weeks. The average effect size from the last 4 visit time points (Weeks 6, 8, 10, and 12) will be the primary comparison between treatments and placebo. These will be averaged after the model has been fit.

Example codes, for the purposes of aiding programming of the primary analysis, using Bayesian MMRM and equivalent frequentist MMRM, are given below.

Bayesian MMRM Model:

```
Proc MCMC data=coa_final nbi=2000 ntu=50 nmc=10000 seed=2019143 thin=10 diag=all

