6.12.3. Secondary Efficacy Analyses

The secondary efficacy outcomes (PDAQ-15, ADAS-Cog₁₃, CDR-CCB PoA, D-KEFS, MoCA, NPI, ESS, and MDS-UPDRS) will be assessed at the 12-week time point as the primary analysis. Each of these secondary endpoints will be analyzed using a frequentist MMRM model, which will include terms for: baseline value, treatment, visit, age, concomitant use of AChEIs, and the relevant interaction terms (treatment by visit, baseline by visit). The change in score from baseline will be the dependent variable. If subscores for a particular scale are deemed clinically relevant to analysis, it will be completed as an exploratory analysis.

For the Alzheimer’s Disease Cooperative Study – Clinician Global Impression of Change (ADCS-CGIC), a logistic regression analysis will be performed with treatment, visit, age, concomitant medication of AChEIs, and relevant interaction terms. Two different endpoints will be assessed: “moderately or better,” defined as subjects who had moderate/marked improvement and “minimally or better” defined as subjects who had minimal/moderate/marked improvement on the ADCS-CGIC scale.

Levodopa equivalency dose (LED) will be calculated using the conversion factors (Tomlinson et al. 2010) of the actual daily dose (mg) of the relevant PD drugs (Table HBEH.6.1). After the LED is calculated for each concomitant medication that a subject is taking, the total LED will be used as a covariate for the analyses of the MDS-UPDRS scales. The impact of LED may be explored for various efficacy and safety measures.

Table HBEH.6.1. LED Conversion Factors

Medication	Multiplication Factor
Immediate release L-dopa dose	1
Controlled release L-dopa dose	0.75
*Entacapone	LD × 0.33
*Tolcapone	LD × 0.5
Duodopa	1.11
Pramipexole (as salt)	100
Ropinirole	20
Rotigotine	30
Selegiline – oral	10
Selegiline – sublingual	80
Rasagiline	100
Amantadine	1
Apomorphine	10

Abbreviation: LED = levodopa equivalency dose.

Note: *LD represents immediate release L-dopa dose for particular patient.

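### SAP 6.15 fits each subgroup level separately and plans no estimate of the between-level difference; levels sharing the design effect of 0.4 would split on p<0.05 in about 47% of trials per dose

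*SAP*

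**What the plan says.** SAP 6.15 lists three outcomes (CoA, ADAS-Cog13, CGIC) and five subgroup variables: PD therapy, AChEI use, memantine use, mild or moderate cognition by MoCA, and timing of dementia onset. The method is to run the Section 6.12.1 analysis "on subsets of the EPP according to each level of each variable listed above separately". The status is clear: "All subgroup analyses will be considered exploratory, and additional subgroup analyses may be performed as suggested by the data".

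The Section 6.12.1 model contains fixed effects "with the interaction terms (treatment by visit, baseline value by visit) with repeated measures of visit within subject". It has no subgroup term.

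Protocol 10.3.6.1 opens "The CDR-CCB CoA and its component scores will be assessed based on the following subgroups" and likewise names no interaction or contrast. Its list differs: it includes PDD or DLB and a GDS cut-off.

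For ADCS-CGIC, SAP 6.12.3 specifies a different model: "a logistic regression analysis will be performed with treatment, visit, age", applied to two responder definitions.

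SAP 6.2 says that MMRM analyses will present LS mean differences, 95% intervals and p-values unless stated otherwise. SAP 6.7 makes no multiplicity adjustment.

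**The concern.** A subgroup analysis asks whether the treatment effect differs between levels. Separate fits answer another question, namely whether the effect can be distinguished from zero within each level. With a fraction of the sample in each fit, one interval can easily exclude zero while the other does not, even when the true effects are equal. Placing the two results side by side invites a reading of heterogeneity that the data do not support.

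The question matters in this trial. Protocol 5.4 justifies enrolling PDD and DLB together on the expectation that they respond alike, and randomization is balanced on AChEI use. Whether effects are alike is a question about a difference and its interval, and the plan produces neither.

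The cross-reference to Section 6.12.1 also fails for some of the analyses it is meant to cover.

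**Working it through.** **Inputs**
- N: "Approximately 750 subjects will be screened to achieve 340 randomized subjects" (SAP 5.2). Allocation 1:1:1:1 gives 340/4 = 85 per arm; 20% discontinuation gives 0.8 × 85 = 68 at Week 12.
- Effect: "the effect size of 0.4 in this study corresponds to a mean difference of 7.2 units" (SAP 5.2).
- Cited rivastigmine difference and SD: "estimated as 5.7 units and 18 units, respectively", so 5.7/18 = 0.317.
- Assumed, because the documents give neither for subgroups: two-sided 0.05 (suggested by the 95% intervals in SAP 6.2) and an equal split. Ranges are shown below.

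**The plan's own figures.** 7.2/18 = 0.40. For the blood pressure precision, 1.96 × 15 × √(2/85) = 4.51 (stated <4.7) and 1.96 × 10 × √(2/68) = 3.36 (stated <3.5). These support 85 and 68 per arm. The stated probability above 80% cannot be reproduced, because the success criterion is redacted and the figure came from simulation with a model across doses. Nothing below depends on it.

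**Separate fits, same true effect d (in SD units) in both levels.** With n per arm in a level:
- SE = √(2/n)
- p = Φ(d/SE − 1.96) + Φ(−d/SE − 1.96)
- P(exactly one level significant) = p1(1 − p2) + p2(1 − p1)

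Equal halves give n = 34 and SE = √(2/34) = 0.2425. At d = 0.4, d/SE = 1.649, so p = Φ(−0.311) + Φ(−3.609) = 0.378. Discordance is 2 × 0.378 × 0.622 = 0.470.

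| True effect in both levels | Power per level | Exactly one level p<0.05 |
|---|---|---|
| 0 | 0.050 | 9.5% |
| 0.2 | 0.131 | 22.7% |
| 0.317 | 0.257 | 38.2% |
| 0.4 | 0.378 | 47.0% |
| 0.5 | 0.540 | 49.7% |
| 0.6 | 0.696 | 42.3% |

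**Sensitivity at 0.4.** With 68 per arm, a 60/40 split gives 47.7%, 70/30 gives 49.8%, 80/20 gives 53.2% and 90/10 gives 57.7%. With 85 per arm the rate runs from 49.6% (50/50) to 58.3% (80/20). One-sided 5% with equal halves and 68 per arm gives 50.0%.

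**All doses, and direction.** A simulation of 400,000 trials with a shared placebo group and a true effect of 0.4 at every dose gave at least one dose discordant on a single variable in 80% (50/50) to 83% (80/20). Estimates of opposite sign occurred in only about 9% to 16% per dose.

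**Interaction contrast.** With equal true effects it declares a difference 5% of the time whatever the effect or split (simulated 4.9% to 5.1%). For equal halves its SE is √(0.2425² + 0.2425²) = 0.343, so the 95% half-width is 1.96 × 0.343 = 0.67 SD, or 0.67 × 18 = 12.1 CoA units. Its power for 0.4 in one level and 0 in the other is about Φ(0.4/0.343 − 1.96) = Φ(−0.79), or 21%.

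**Does Section 6.12.1 fit the listed analyses?**
- *CGIC.* Section 6.12.1 models change from a baseline value. ADCS-CGIC is itself a seven-point rating of change (protocol 9.1.2.1.1), and the Schedule of Activities has only the interview at Visit 2, with no rating. SAP 6.12.3 gives it logistic regression.
- *ADAS-Cog13.* The Section 6.12.1 primary comparison averages Weeks 6, 8, 10 and 12. The scheduled on-treatment visits for ADAS-Cog13 are Visits 8 and 11, which are Weeks 6 and 12.
- *AChEI subgroup.* AChEI use is a covariate in Section 6.12.1 and is constant within each AChEI subset, so only the diffuse priors separate its coefficient from the intercept.

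**The case against.** The analyses are optional and exploratory, and the SAP sets no threshold or consistency rule for them. A reader might infer that the plan will declare heterogeneity whenever one level passes and the other fails. The documents do not say so; that comparison is a likely misreading of the output, not a planned step. This stands, and it limits the severity.

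A reader might also infer that separate fits make the difference unobtainable. They do not. The levels contain different subjects, so the two estimates can be subtracted and their standard errors or posterior draws combined. The gap is that no one is told to do this or report it.

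Separate fits do let covariances and covariate slopes differ by level, which may be sensible for mild versus moderate cognition. Forcing a shared covariance is therefore optional. SAP 6.2 also allows other covariance structures if the unstructured one fails, and failure in subsets has not been shown.

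Finally, the interaction test is weak. With about 21% power for 0.4 versus 0, a null result could be misread as consistency. This is right, and it is why the estimate and interval matter more than the test.

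**Conclusion.** The gap is real and minor. The subgroup method in SAP 6.15 does not estimate the difference in effect, and its reference to Section 6.12.1 cannot be followed for CGIC or carried over unchanged to ADAS-Cog13 and the AChEI subgroup.

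The size is about 47% discordance on p<0.05 per dose, against 5% for a contrast. That rests on a true effect of 0.4 in both levels, two-sided 0.05, equal halves, 68 per arm and a simple two-sample comparison. For CoA, p<0.05 stands in for a 95% credible interval excluding zero. The Weeks 6 to 12 average in a covariate-adjusted model may be more precise than assumed here, which would shift the figures.

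Two stronger readings are not supported. One is that identical effects look discordant about half the time as a general rule: the rate falls to about 38% at 0.317, 23% at 0.2 and 9.5% at zero, and it concerns significance, not direction. The other is that these results will set the next trial's population. The documents do not say that, and SAP 6.2 does not expect exploratory analyses in the study report unless they bear on the conclusions.

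**What to change.** Rewrite the method sentence in SAP 6.15:
- **CoA and ADAS-Cog13:** fit one model to the whole EPP with treatment-by-subgroup-by-visit and all lower-order terms, with a shared or level-specific covariance. Report each level's effect and the between-level difference with its 95% interval.
- **ADAS-Cog13:** use the Week 12 contrast, not the Weeks 6 to 12 average.
- **CGIC:** refer to the Section 6.12.3 logistic model with the same interaction added.
- **AChEI subgroup:** let the existing AChEI covariate serve as the subgroup main effect, so that it is not entered twice.
- **Interpretation:** keep the exploratory label, and state that the interaction test has low power and that a non-significant result is not evidence of consistency.

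The cost is a paragraph of SAP text and a few model terms; no new data are needed. SAP Version 3 was approved after unblinding (SAP Section 3), so a change made now should be dated and labelled as post-unblinding.
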